## 10.1 General

Smith+Nephew's Global Biostatistics group or designee will conduct the statistical analysis for this study. Unless otherwise stated, all significance tests will be two-sided, performed at the 5% significance level. Resulting p-values will be quoted. Point estimates and their corresponding 95% two-sided confidence intervals will be generated where appropriate. Where data summaries are specified, categorical and ordinal variables will be summarized with frequencies and percentages. Continuous variables will be summarized with the following summary statistics: number of observations, mean, median, standard deviation, minimum, and maximum values. All analyses will be performed in SAS 9.4 (or later).

## 10.2 ANALYSIS POPULATIONS

The following analysis populations will be used for this study:

- Safety population (SAF): This includes all patients who have received the study device.
- Full Analysis Set (FAS): This includes all patients who were recruited into the study and have at least one post-baseline visit.
- Per-Protocol (PP) population: This includes all subjects in the FAS who have no significant protocol deviations and who meet all the inclusion/exclusion criteria.

Statistical analysis will be performed using each of the patient populations as follows: Analysis of the primary and secondary endpoints will be performed separately using both the FAS and PP populations. All safety analyses will utilize the SAF population.

This document contains information that is confidential and proprietary to Smith + Nephew PLC and Smith + Nephew, Inc. and is intended for use only by Smith + Nephew and its manufacturer. It shall not be reproduced or copied in whole or in part, nor shall the contents be disclosed by any means without prior written permission from Smith + Nephew, nor shall anyone make any use of it that is contrary to the expressed or implied wishes of Smith + Nephew.

Study Protocol	> ∕ smith&nephew
A prospective, multi-center, single arm PMCF study to evaluate the safety and performance of ENTACT™ (Next Generation) resorbable septal staple system for septoplasty	Number: ENTACT.ENT.PRO.SEP.2019.05
	Version: 2.0, 27Aug2020
	Page: Page 55 of 94

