### CONFIDENTIAL AND PROPRIETARY

Study Protocol	% smith&nephew
A prospective, multi-center, single arm PMCF study to evaluate the safety and performance of ENTACT™ (Next Generation) resorbable septal staple system for septoplasty	Number: ENTACT.ENT.PRO.SEP.2019.05
	Version: 2.0, 27Aug2020 Page: Page 24 of 94

devices for the Sainio study. In Sowerby et al., the authors concluded that the septal stapler can be used without an increased morbidity in comparison to suture closure or impact to subjective patient scores.

Tami et al. reported that the first lot of ENTACT Septal Staplers (2009) failed to perform to design specifications and only four total staples from three staplers were implanted in one patient.

Sainio et al. observed haematoma in one patient in the ENTACT Stapler group. Sainio et al. reported that perforation and haematoma, which occurred at a low rate of 1% each in the study, is in agreement with the study conducted by Tami et al. and stated that "ENTACT Septal Stapler is safe to use". The complications reported in the four studies of the ENTACT stapler are performing in-line with alternative devices on the market as discussed in the State of the Art.

Some of the minor complications observed in the literature were edema, inflammation and infection. Sowerby et al. conducted a prospective, randomized clinical study comparing ENTACT Septal Stapler to quilting sutures in patients undergoing septoplasty. Sowerby et al observed mild edema in 2 patients in both the groups at a 3 week follow up. However, the edema resolved in 2 months. In a prospective, case series, mild inflammation was reported at a 1 week follow up in 21% of the patients in whom ENTACT Septal Stapler was used for approximation of mucoperichondrial flaps after septoplasty whereas no inflammation was observed in 79% of the patients. Expected rates of edema or inflammation following septoplasty were not discussed in the four publications identified. Other complications reported in the literature include bleeding, and fever.

Sainio et al. conducted a retrospective comparative study comparing ENTACT Septal Stapler to the non-stapler group where silicone splints, tamponade, or sutures were used during septoplasty. No significant difference in the complication rate was observed between the

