## 10.4.2 Analysis of Secondary Endpoints

Nasal cavity assessments at day 5 and day 42 will be summarized and presented as count and percentage of each criterion.

Successful staple deployment at the operative visit will be summarized by count and percentage. A 95% exact confidence interval for a single proportion will be presented for successful staple deployment using the Clopper-Pearson method. The number of staples used and whether the stapler misfired will also be presented.

Total operating room time will be calculated and summarized using descriptive statistics and will be presented descriptively by septoplasty only cases as well as septoplasty and turbinate reduction cases.

Intra-operative time to deploy staples to complete septoplasty, calculated as time between start of closure to when the stapler was handed back to the scrub nurse, will be summarized and presented descriptively by septoplasty only cases as well as septoplasty and turbinate reduction cases.

NOSE score will be calculated and summary statistics will be presented by visit. Change in NOSE score from the pre-operative visit to each post-operative visit will also be presented and an ANOVA model will be used to assess statistical significance.

This document contains information that is confidential and proprietary to Smith + Nephew PLC and Smith + Nephew, Inc. and is intended for use only by Smith + Nephew and its manufacturer. It shall not be reproduced or copied in whole or in part, nor shall the contents be disclosed by any means without prior written permission from Smith + Nephew, nor shall anyone make any use of it that is contrary to the expressed or implied wishes of Smith + Nephew.

Study Protocol	% smith&nephew
A prospective, multi-center, single arm PMCF study to evaluate the safety and performance of ENTACT™ (Next Generation) resorbable septal staple system for septoplasty	Number: ENTACT.ENT.PRO.SEP.2019.05
	Version: 2.0, 27Aug2020
	Page: Page 57 of 94

The VAS Pain score will be summarized by visit. Change in VAS Pain score from the preoperative visit to each post-operative visit will also be presented and an ANOVA model will be used to assess statistical significance.

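### Surgery-day device results are assigned to the FAS and PP, which can leave out treated patients; they belong in the set of all patients in whom the stapler was used or attempted

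*Combined protocol and SAP*

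**What the plan says.** Section 10.2 defines three sets and allots endpoints to them.

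- "Safety population (SAF): This includes all patients who have received the study device". There is no visit condition. Its only stated use is safety: "All safety analyses will utilize the SAF population".
- "Full Analysis Set (FAS): This includes all patients who were recruited into the study and have at least one post-baseline visit". The protocol does not say which visits satisfy this condition.
- "Per-Protocol (PP) population: This includes all subjects in the FAS who have no significant protocol deviations and who meet all the inclusion/exclusion criteria". The PP is a subset of the FAS and inherits its visit condition.
- "Analysis of the primary and secondary endpoints will be performed separately using both the FAS and PP populations". No exception is made for operative data.

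Section 10.4.2, on secondary endpoints, includes staple deployment: "A 95% exact confidence interval for a single proportion will be presented for successful staple deployment using the Clopper-Pearson method". The same section presents staples used, misfires, total operating time and closure time, and names no other population. Section 9.1.2 has delivery success and both times recorded at Visit 2, the day of surgery.

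Three further places bear on who stays in each set. Section 7.3 applies the exclusion criteria at screening and also during surgery, and criterion 2 is a need for conventional suturing. Section 7.6 counts a subject as enrolled once consented and treated. The notes to Table 9.1.1-1 end participation and data collection at a re-intervention on the implant.

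**The concern.** These results are known for every treated patient before any follow-up visit takes place. Making their analysis depend on later attendance, or on a later judgement about protocol compliance, removes observed data and gains nothing.

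The removal need not be random. A re-intervention before the Day 5 visit would leave a patient with no follow-up visit. A stapling that had to be finished with sutures can be read as meeting exclusion criterion 2, which would take that patient out of the PP because of the deployment failure itself.

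Section 6.1.3 says that the implant is unchanged and that the changes are in the delivery part of the device. Deployment success and closure time therefore bear directly on what is new. Closure time also bears on the proposed claim in section 5.4 of closure in under a minute.

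**Working it through.** **Inputs.** 40 enrolled, 10% dropout and 36 evaluable (section 11); Clopper-Pearson 95% intervals (section 10.4.2). The documents give no deployment failure rate, so the failure counts below are assumptions, shown over a range.

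**The plan's own figures.** 36/(1 − 0.10) = 40, as stated, so planned dropout is 40 × 0.10 = 4 patients. Table 4.4.1-1 gives exact intervals of 0.6% to 16.92% for 2/40 and 2.8% to 23.7% for 4/40. Subtracting from 100 gives 83.1% to 99.4% for 38/40 and 76.3% to 97.2% for 36/40, which agree with the direct calculation.

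**Formula.** For x successes in n, the lower limit L solves P(X ≥ x | L) = 0.025 and the upper limit U solves P(X ≤ x | U) = 0.025. When x = n, L = 0.025^(1/n) and U = 1. For n = 38, L = 0.025^(1/38) = 0.907. For n = 36, L = 0.025^(1/36) = 0.903.

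**All treated against those who return** (rate, 95% CI):

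| Failures in 40 | All treated | Never return | Failures among them | Reported |
|---|---|---|---|---|
| 2 | 38/40 = 95.0% (83.1 to 99.4) | 2 | 0 | 36/38 = 94.7% (82.3 to 99.4) |
| 2 | same | 2 | 1 | 37/38 = 97.4% (86.2 to 99.9) |
| 2 | same | 2 | 2 | 38/38 = 100% (90.7 to 100) |
| 3 | 37/40 = 92.5% (79.6 to 98.4) | 4 | 0 | 33/36 = 91.7% (77.5 to 98.2) |
| 3 | same | 4 | 1 | 34/36 = 94.4% (81.3 to 99.3) |
| 3 | same | 4 | 2 | 35/36 = 97.2% (85.5 to 99.9) |
| 3 | same | 4 | 3 | 36/36 = 100% (90.3 to 100) |

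**If loss is unrelated to deployment.** The rate is unchanged on average. With 3 failures and 4 lost at random, the chance that no failure is among the lost is C(37,4)/C(40,4) = 66,045/91,390 = 72%. The rate then moves from 92.5% to 91.7%, a fall of 0.8 points, and the interval widens slightly.

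**If loss is related.** The rate rises, to 100% at the extreme, and the lower limit rises from 83.1% to 90.7% (2 failures, both lost) or from 79.6% to 90.3% (3 failures, all lost).

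**PP with full follow-up.** If all 40 return but 2 failed staplings were converted to suture and judged to meet exclusion criterion 2, the PP also reads 38/38 where all treated gives 38/40. This does not depend on what a post-baseline visit means.

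**Operative times.** The documents give no distribution for the new device, so no size is computed. If difficult cases are the ones lost, the bias is towards shorter times.

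**The case against.** Several points on the other side are sound.

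- **The visit term is undefined.** Eligibility is set at the baseline screening, and surgery is itself a numbered visit, so Visit 2 could count as post-baseline. If recruited means consented, the condition would then remove only those who never reached surgery, and no treated patient would leave the FAS. Against this, section 7.6 makes treatment part of enrolment. If recruited means enrolled, that reading leaves the condition empty. The text does not settle it, so the FAS part of the point is conditional. The PP part is not.
- **Failures need not disappear.** A reader might infer that a failed deployment in a non-returner goes unreported. That is not supported: device deficiencies include malfunctions and use errors (12.1.6) and are summarised by number and by patient in the safety population (10.5). What can be affected is the deployment rate, its interval and the operative times.
- **The illustration is extreme.** Leaving the FAS means missing all three follow-up visits. The 10% is total planned dropout, and nothing in the documents links non-return to failed deployment.
- **No formal decision depends on it.** Deployment success is absent from the list in 8.3.2 and has no acceptance threshold. Section 8.3.2 asks for the times in the full population, but that term is undefined and does not override 10.2.

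A reader might also infer from the earlier-generation case in section 4.2.2, where "only four total staples from three staplers were implanted in one patient", that a case needing several staplers could pass unnoticed as delivered. The documents do not support this. Section 9.1.2 also records stapler identifiers (such as the unique device identifier, lot and serial number), and 10.4.2 presents misfires. Nor do they support any particular scoring rule based on the first stapler opened.

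**Conclusion.** The point holds in a limited form. As written, 10.2 places surgery-day results in sets that can exclude patients in whom they were fully observed. For the FAS, this rests on reading a post-baseline visit as a follow-up visit, which is the natural reading but not a stated one. For the PP, it holds on either reading, provided that a conversion to suture is judged to meet exclusion criterion 2.

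The effect is typically about 1 point or less if loss is unrelated to deployment. It favours the device if failures are over-represented among those lost, and the change from 95.0% to 100% is an upper illustration on assumed counts. The correction is still worth making, because it removes the selection at almost no cost.

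**What to change.** In section 10.2, or in the SAP that section 10 says will be finalised before database lock:

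1. State that deployment success, staples used, misfires, closure time and total operation time are analysed primarily in all patients in whom the study device was used or attempted, with FAS and PP as supportive.
2. Clarify that the safety population includes attempted deployments. Its definition turns on having received the device, so a patient in whom no staple could be placed might otherwise be left out.
3. Define a post-baseline visit as a follow-up visit after surgery.

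The cost is a few sentences, with no new data collection and no added burden on patients. The one downside is that the reported deployment rate may be slightly less favourable.

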## 10.3 BASELINE DATA

Data to be summarized at baseline includes but is not limited to all collected demographic variable such as age, gender, primary diagnosis, height, weight, Body-Mass-Index and medical history. The baseline variables will be used to describe the outcome data where necessary.

### 10.4 EFFICACY ANALYSIS

## **10.4.1 Analysis of Primary Endpoint**

Data will be collected on whether the septum wall appearance and need for re-intervention at the surgery site are due to the device or the procedure. Only those that are device-related will contribute to the primary endpoint analyses, in line with the primary objective of this study. A binary variable will be defined as follows; one if all five of the following criteria are true and 0 if at least one of the criteria is false:

- Septum wall straight appearance
- Complete coaptation of perichondrial flaps on septum wall
- Absence of significant local tissue reaction at the staple site
- Absence of hematoma swelling at the staple site
- No need for re-intervention at the surgery site

Clinical success will be inferred for a patient if their binary variable is 1. Clinical success will be reported as a count and percentage with a 95% CI using Clopper-Pearson Exact methodology. A logistic model will be used to evaluate the adjusted and unadjusted models for the primary outcome variable. The variables considered important and to be included in the final model are age and BMI. All other baseline and medical factors collected at baseline will be evaluated for

This document contains information that is confidential and proprietary to Smith + Nephew PLC and Smith + Nephew, Inc. and is intended for use only by Smith + Nephew and its manufacturer. It shall not be reproduced or copied in whole or in part, nor shall the contents be disclosed by any means without prior written permission from Smith + Nephew, nor shall anyone make any use of it that is contrary to the expressed or implied wishes of Smith + Nephew.

Study Protocol	Smith&nephew
A prospective, multi-center, single arm PMCF study to evaluate the safety and performance of ENTACT ™ (Next Generation) resorbable septal staple system for septoplasty	Number: ENTACT.ENT.PRO.SEP.2019.05
	Version: 2.0, 27Aug2020
	Page: Page 56 of 94

importance in adjusted models and only those statistically significant in an unadjusted model will be considered in the final model.

This analysis will be carried out using the FAS as the primary analysis population and the PP population using for sensitivity analysis.

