Exclusion Criteria:	The patient will be ineligible for the study if he or she meets any of the
	following exclusion criteria at the baseline screening or during
	surgery:
	1. Prolonged tissue approximation beyond that needed for
	normal tissue closure is necessary or desired;
	2. Traditional suturing techniques is necessary;
	3. Radiopacity is necessary or desired since ENTACT septal
	staples are radiotransparent;
	4. Known to be allergic to foreign body of materials of
	investigational product;
	5. Concomitant procedures other than turbinectomy, turbinate
	reduction, and/or sinus surgery;
	6. Pregnancy at time of the procedure;
	7. Presence of infection at the site;
	8. Severe drug and alcohol abusers;
	9. Autoimmune disease deemed clinically significant by Principal
	Investigator (PI).

Study Protocol	St smith&nephew
A prospective, multi-center, single arm PMCF study to evaluate	Number:
the safety and performance of ENTACT™ (Next Generation)	ENTACT.ENT.PRO.SEP.2019.05
resorbable septal staple system for septoplasty	Version: 2.0, 27Aug2020
	Page: Page 8 of 94

Study Duration:	Estimated 8 months from first study site initiation to last subject last visit. Estimated enrollment period: 6 months Follow up period: 6 weeks		
Primary endpoint:	At the 21-day follow-up visit, the clinician will examine the patient's nasal cavity and will confirm:		
	
 
Septum wall straight appearance (yes/no);
 
		
	
 
Complete coaptation of perichondrial flaps on septum wall (yes/no);
 
		
	
 
Absence of significant local tissue reaction at the staple site (yes/no);
 
		
	
 
Absence of hematoma swelling at the staple site (yes/no);
 
		
	
 
No need for re-intervention at the surgery site (yes/no);
 
If all the answers to the questions above are "YES" then clinical
 
		
	success will be inferred (if any answer is "NO" then repair failure will		
	be inferred).		
Secondary endpoint(s):	• At the 5 and 42-day follow-up visit, the clinician will examine		
	the patient's nasal cavity and will confirm:		
	
 
Septum wall straight appearance (yes/no);
 
		
	
 
Complete coaptation of perichondrial flaps on septum
 
		
	wall (yes/no);		
	
 
Absence of significant local tissue reaction at the staple site (yes/no);
 
		
	Absence of homotome eventing at the starts site		
	(ves/no).		
	$\circ$ No need for re-intervention at the surgery site (yes/no).		

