# 4. INTRODUCTION

# 4.1 BACKGROUND

In addition to olfaction, one of the main functions of the nasal passage is to provide airflow. Nasal airways may become obstructed, which necessitates treatment to address the blockage. Nasal airway obstruction may be caused by mucosal or structural defects resulting from trauma, idiopathic disease, or iatrogenic side effects. Anatomical deformities may occur in the septum, turbinates, or nasal valve.

Septal deviation is one of the most common and prevalent problems in otorhinolaryngology. A deviated septum can cause nasal obstruction and is commonly treated using septoplasty. Nasal valve dysfunction may be associated with up to 13% of cases of nasal obstruction and is also involved in up to 95% of cases of persistent nasal obstruction after septoplasty. Repairing a deviated septum can be done through a surgery called septoplasty. During surgery, the deviated cartilage and bone are removed from the septum, leaving a dead space. Septoplasty involves elevation of subperichondrial/periosteal flaps bilaterally as well as resection and/or reshaping of the deviated cartilage and/or bone. The space created between the flaps during this procedure must be coapted in order to prevent septal hematoma and other complications such as abscess formation, septal perforation, or saddle-nose deformity, and separation of blood supply from the cartilage.

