# 5.1 **PRIMARY OBJECTIVE**

The primary objective of this study is to demonstrate clinical success of the ENTACT (Next

Generation) resorbable septal staple system by examining the patient's nasal cavity at the 21

day follow up visit.

This document contains information that is confidential and proprietary to Smith + Nephew PLC and Smith + Nephew, Inc. and is intended for use only by Smith + Nephew and its manufacturer. It shall not be reproduced or copied in whole or in part, nor shall the contents be disclosed by any means without prior written permission from Smith + Nephew, nor shall anyone make any use of it that is contrary to the expressed or implied wishes of Smith + Nephew.

Study Protocol	> ∕ smith&nephew
A prospective, multi-center, single arm PMCF study to evaluate the safety and performance of ENTACT ™ (Next Generation)	Number: ENTACT.ENT.PRO.SEP.2019.05
resorbable septal staple system for septoplasty	Version: 2.0, 27Aug2020
	Page: Page 27 of 94

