### 8.3 **STUDY ENDPOINTS**

#### 8.3.1 Primary Endpoint

At the 21-day follow-up visit, the clinician will examine the patient's nasal cavity and will confirm:

- Septum wall straight appearance (yes/no);
- Complete coaptation of perichondrial flaps on septum wall (yes/no);
- Absence of significant local tissue reaction at the staple site (yes/no);
- Absence of hematoma swelling at the staple site (yes/no);
- No need for re-intervention at the surgery site (yes/no);

If all the answers to the questions above are "YES" then clinical success will be inferred (if any answer is "NO" then repair failure will be inferred).

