## 8.3.3 Safety Endpoints

Following are the safety endpoints for this study:

- Device-related re-intervention;
- All adverse events (AEs) occurring from the time of surgery until re-intervention or study completion;
- Device related AEs (ADEs) and serious adverse events (SAE's);
- Device deficiencies (DDs)

All AEs will be categorized in terms of seriousness and relatedness to the study device or to the surgical procedure. All Serious Adverse Device Effects will be further categorized as Anticipated or Unanticipated. The definitions for each of these categories are based on ISO 14155:2011.

This document contains information that is confidential and proprietary to Smith + Nephew PLC and Smith + Nephew, Inc. and is intended for use only by Smith + Nephew and its manufacturer. It shall not be reproduced or copied in whole or in part, nor shall the contents be disclosed by any means without prior written permission from Smith + Nephew, nor shall anyone make any use of it that is contrary to the expressed or implied wishes of Smith + Nephew.

Study Protocol	> ∕ smith&nephew
A prospective, multi-center, single arm PMCF study to evaluate the safety and performance of ENTACT™ (Next Generation) resorbable septal staple system for septoplasty	Number: ENTACT.ENT.PRO.SEP.2019.05
	Version: 2.0, 27Aug2020
	Page: Page 45 of 94

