#### 8.3.7 Pre-specification of Statistical Analysis

The primary outcome measure has been pre-specified as well as the type of statistical analysis to be performed to evaluate procedure success rate so as to minimize reporting bias. The precision analysis planned for the study, which includes construction of confidence intervals for the outcome summaries and a pre-defined range in which the 95% CI for the primary outcome are expected to fall within are designed to maximize the validity of the study results.

More detailed information on analyses to be carried out will be incorporated in the Statistical Analysis Plan (SAP) so as minimize any threats to external validity in order to yield clinically relevant estimates of effects and precision.

This document contains information that is confidential and proprietary to Smith + Nephew PLC and Smith + Nephew, Inc. and is intended for use only by Smith + Nephew and its manufacturer. It shall not be reproduced or copied in whole or in part, nor shall the contents be disclosed by any means without prior written permission from Smith + Nephew, nor shall anyone make any use of it that is contrary to the expressed or implied wishes of Smith + Nephew.

Study Protocol	% smith&nephew	
A prospective, multi-center, single arm PMCF study to evaluate the safety and performance of ENTACT™ (Next Generation) resorbable septal staple system for septoplasty	Number: ENTACT.ENT.PRO.SEP.2019.05	
	Version: 2.0, 27Aug2020	
	Page: Page 46 of 94	

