## 12.1.2 Adverse Device Effect

An Adverse Device Effect (ADE) is an adverse event that, in the opinion of the investigator, is related to the use of the IP.

Note 1: This definition includes adverse events resulting from insufficient or inadequate instructions for use, deployment, implantation, installation or operation, or any malfunction of the investigational medical device.

Note 2: This definition includes any event resulting from use error or from intentional misuse of the investigational medical device.

- **Not Related** An AE is considered to be not related to the use of an IP or the procedure when the effect is DEFINITELY UNRELATED or UNLIKELY to have any relationship to the use of the IP or the procedure;
- **Related** An AE is considered to be related to the use of an IP or the procedure when there is a POSSIBLE, PROBABLE, or DEFINITE relationship between the AE and the use of the IP or the procedure.

An ADE is further categorized depending on whether the criteria in **section 12.1.3 and 12.1.4** are met.

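### Section 10.4.1 counts two of the five primary-endpoint items only when device-related, which conflicts with Sections 2 and 8.3.1 and with its own binary variable

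*Combined protocol and SAP*

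**What the plan says.** Section 8.3.1 lists five yes/no items at the 21-day visit: straight septum, complete flap coaptation, no significant local tissue reaction, no hematoma swelling, and no need for re-intervention at the surgery site. Its rule is "if any answer is 'NO' then repair failure will be inferred". The Synopsis states the same rule. Neither place mentions cause.

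Section 10.4.1 opens by saying that the cause of the septum-appearance and re-intervention findings, device or procedure, will be recorded. It adds: "Only those that are device-related will contribute to the primary endpoint analyses, in line with the primary objective of this study". The next sentence sets the binary variable to 1 if all five items are true and 0 if any is false, and lists the items without qualification.

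The objective that the filter relies on, in Section 5.1, begins "The primary objective of this study is to demonstrate clinical success of the ENTACT". It goes on to name the nasal examination at day 21 and makes no distinction by cause. Where the narrower event is meant, the protocol names it: Section 8.3.3 lists "Device-related re-intervention" as a separate safety endpoint.

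**The concern.** One primary endpoint has two rules, and the same data can give two success rates. Section 10.4.1 also leaves the filter incomplete, because it does not say whether a procedure-attributed NO becomes a met criterion or takes the subject out of the analysis. It gives no criteria for telling device from procedure and does not say who decides.

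The adverse-event text does not settle this. Sections 8.3.3 and 12.3 ask for relatedness to the device and to the procedure. The scale in Section 12.1.2, however, calls an event "considered to be related to the use of an IP or the procedure when there is a POSSIBLE, PROBABLE, or DEFINITE relationship", and Table 12.1-1 also pools the two.

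At stake are the headline success rate and its confidence interval. The study is open-label, and the only movement the filter allows is upward.

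**Working it through.** **Inputs**

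- All-cause rule: Sections 2 and 8.3.1.
- Filter on two of the five items: Section 10.4.1.
- Interval: two-sided 95% Clopper-Pearson (Section 10.4.1).
- n: 36 evaluable and 40 enrolled (Section 11). The dropout step reproduces: 36 / (1 − 0.10) = 40.
- f, the number of all-cause failures: assumed, 1 to 6. The plan gives no day-21 composite failure rate. The 92% in Section 11 is fixation of tissue at one week.
- a, the number of affected subjects: those whose only NO is on one or both filtered items and is attributed to the procedure. Assumed 0, 1 or 2.

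**Step 1: the texts side by side**

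| Place | Does a procedure-caused NO on septum or re-intervention count as failure? |
|---|---|
| Section 2 | Yes |
| Section 8.3.1 | Yes |
| 10.4.1, filter sentence | No |
| 10.4.1, binary variable | Yes |

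**Step 2: direction**

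The filter acts only on a NO. A subject with a second NO on an unfiltered item still fails. So failures can be taken away but not added.

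**Step 3: formulas**

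- All-cause: (n − f) / n
- Recoded as met: (n − f + a) / n
- Removed: (n − f) / (n − a)
- Lower limit for x successes in m subjects: the 0.025 quantile of Beta(x, m − x + 1)

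**Step 4: n = 36, one affected subject.** Entries are estimate (lower limit) in percent. Differences are taken before rounding.

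| f | All-cause | Recoded | Rise in lower limit | Removed | Rise in lower limit |
|---|---|---|---|---|---|
| 1 | 97.22 (85.47) | 100.00 (90.26) | 4.8 | 100.00 (90.00) | 4.5 |
| 2 | 94.44 (81.34) | 97.22 (85.47) | 4.1 | 97.14 (85.08) | 3.7 |
| 3 | 91.67 (77.53) | 94.44 (81.34) | 3.8 | 94.29 (80.84) | 3.3 |
| 4 | 88.89 (73.94) | 91.67 (77.53) | 3.6 | 91.43 (76.94) | 3.0 |
| 5 | 86.11 (70.50) | 88.89 (73.94) | 3.4 | 88.57 (73.26) | 2.8 |
| 6 | 83.33 (67.19) | 86.11 (70.50) | 3.3 | 85.71 (69.74) | 2.6 |

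The estimate rises by 1/36 = 2.8 points if recoded, and by 2.4 (f = 6) to 2.8 (f = 1) if removed. At n = 40, recoding adds 1/40 = 2.5 points to the estimate and 3.0 to 4.3 to the lower limit.

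**Step 5: n = 36, two affected subjects, f from 2 to 6**

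- Recoded: the estimate rises by 2/36 = 5.6 points. The lower limit rises by 8.9 (f = 2, 81.34 to 90.26) down to 6.8 (f = 6, 67.19 to 73.94).
- Removed: the lower limit rises by 8.4 (f = 2, 81.34 to 89.72) down to 5.4 (f = 6, 67.19 to 72.55).

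Example with f = 4 and a = 2: all-cause 32/36 = 88.9% (73.9 to 96.9); recoded 34/36 = 94.4% (81.3 to 99.3); removed 32/34 = 94.1% (80.3 to 99.3).

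With a = 0 nothing changes.

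**The case against.** The filter has a clinical rationale. Section 4.1 describes septoplasty as "resection and/or reshaping of the deviated cartilage and/or bone", whereas Section 6.1.1 gives the stapler the task of approximating the flaps. A septum that is not straight may therefore say little about the device. The objective does concern success of the ENTACT system, and the contradiction could also be removed by qualifying Sections 2 and 8.3.1. This stands as a reason to report a device-attributed rate. It does not justify leaving two rules in force. The phrase in Section 8.3.7, "to evaluate procedure success rate so as to minimize reporting bias", leans towards an all-cause reading, but it is passing wording and I give it little weight.

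Four stronger readings are tempting, and the documents do not support them.

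- *The definition could be chosen after outcomes are known.* A reader might infer this because the SAP is due only before database lock and Section 10.6 allows activity reports. But the filter is already in Version 2.0, which takes effect before enrollment (Section 21.1.3), and Section 10 requires the SAP and study report to disclose changes.
- *The operating surgeon judges the result.* Section 8.4.3 gives follow-up exams to investigators not involved in the procedure. It does not say who attributes cause.
- *The protocol has no text separating device from procedure.* Sections 8.3.3 and 12.3 ask for both. The text is mixed, not absent.
- *The filter could turn a failed study into a success.* No success-rate threshold is stated. Section 8.3.7 mentions a range set in advance for the interval, but the only number given is the ±11% precision target in Section 11.

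**Conclusion.** The concern holds as a conflict in current text. Sections 2 and 8.3.1, and the binary variable in 10.4.1, are all-cause; one sentence in 10.4.1 is not, and the objective it cites does not contain the restriction. The coding and attribution rules needed to apply that sentence are missing. What remains exposed is subject-level attribution in an open-label study and the unresolved coding.

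The size depends on how many subjects have a sole NO that is procedure-attributed, which the documents cannot tell us. It may be nil, and the tabulated shifts rest on assumed failure counts. One or two such subjects would visibly move an estimate based on 36 to 40 people. This should be fixed, but no pass/fail decision depends on it.

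**What to change.** Before outcomes are seen:

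1. Delete the device-related filter from the primary analysis in Section 10.4.1, so that it matches Sections 2 and 8.3.1 and its own binary variable.
2. State that a re-intervention at the surgery site before the day-21 assessment counts as a failure. The notes to Table 9.1.1-1 end data collection at re-intervention of the implant, so such a subject may have no day-21 exam.
3. Report the device-attributed rate beside the primary result as a labelled sensitivity analysis. Use the same denominator and code a procedure-attributed NO on the two items as met. Name who attributes cause and by what criteria, and say how the unexamined items are coded for a subject with an early procedure-attributed re-intervention.
4. Keep device-related re-intervention as the separate safety endpoint of Section 8.3.3.

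The cost is one sentence deleted, a short coding and attribution rule, and one extra table from data already to be collected. The downside is that the headline rate may be slightly lower and will include failures the stapler did not cause. The device-attributed rate beside it shows how many.
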